# 9 Summary of Study Data

All continuous variables will be summarized using the following descriptive statistics: n (non-missing sample size), mean, and standard deviation. The frequency and percentages (based on the non-missing sample size) of observed levels will be reported for all categorical measures. In general, all data will be listed, sorted by treatment and subject, and when appropriate by visit number within subject. All summary tables will be structured with a column for each treatment in the order (Control, Intervention) and will be annotated with the total population size relevant to that table/treatment, including any missing observations.

# 9.1 Subject Disposition

We establish how many subjects reached the various stages of the trial (Enrollment, Allocation, Follow-up, and Analysis) using the following list:

[figure not shown]
Enrollment:

- Regularly exercise > 60 min/wk
- Scheduled knee replacement
- Received physical therapy or prescribed an exercise program in past 6 months
- Did not receive medical clearance after failing the Adult Pre-Exercise Screening System questionnaire
- < 45 years of age
- No activity related knee pain
- Morning stiffness > 30 min
- Reside outside of the contiguous United States
- Not comfortable with a program delivered in English
- Not seeking to be more physically active
- Did not have a smartphone/ computer with internet access
- Did not complete the baseline data collection

Allocation:

- Did not receive allocated intervention
- Follow-up:
- Lost to Follow-up
- Discontinued the intervention

#### Figure 2: CONSORT Diagram Template

#### Table 4: Anticipated Recruitment Schedule

	ANTICIPATED		
Month	# to Randomize/month	Cumulative Total	
July 2021	1	1	
August 2021	4	5	
September 2021	5	10	
October 2021	6	16	
November 2021	6	22	
December 2021	6	28	
January 2022	6	34	
February 2022	6	40	
March 2022	6	46	
April 2022	6	52	
May 2022	6	58	
June 2022	6	64	
July 2022	6	70	
August 2022	6	76	
September 2022	6	82	
October 2022	6	88	
November 2022	6	94	
December 2022	6	100	

### 9.2 **Protocol Deviations**

Potential protocol deviations include: follow-up assessments collected outside of preset time window, participants delaying assessment due to unforeseen circumstances, or the activity monitors not being sent/being lost in the mail. All would be considered missing data and would be handled in the manner described in the Missing Data section of this document.

### 9.3 Demographic and Baseline Variables

Table 5: Demographic	and Baseline	Characteristics
rabio o. Domographio		onaraotonotioo

Characteristic [mean (sd) or n (%)]	All Study	Intervention (n=)	Control (n=)
	Participants (n=)		
Age (years)			
Weight (kg)			
Height (m)			
Body Mass Index (kg/m  )			
Gender			
Women			
Men			

Non-binary	
Race	
White	
Black	
Asian	
Native American or Alaskan	
Native	
Hawaiian or Pacific Islander	
More than one race	
Ethnicity (n/N)	
Hispanic	
Annual household income (\$)	
< 5,000	
$\geq$ 5,000 to < 25,000	
$\geq 25,000 \text{ to} < 50,000$	
$\geq$ 50,000 to < 75,000	
$\geq 75,000 \text{ to} < 100,000$	
≥ 100,000	
Education	
< High School	
High school	
Associate's degree	
Bachelor's degree	
Master's degree	
Doctoral degree	
Other	
Number of comorbidities	
Work	
Full-time	
Part-time	
Unemployed or laid off	
Retired	
Keeping house or raising	
children	
Community Type	
Rural	
Urban	

#### **Treatment Compliance**

#### Table 6: Treatment Compliance Measures

Table 0. Treatment Compliance Measures	Control		
	-	Intervention	
Number of physical therapy consultations (0-5), mean (SD)	_		
Number of physical therapist consultations, n (%)			
0	-		
1	-		
2	-		
3	-		
4	-		
5	-		
Duration of physical therapist consultations (mins), mean (SD)			
Initial	-		
Follow-ups	-		
PT discussed steps/day n/N (%)			
1 st consultation	-		
2 nd consultation	-		
3 rd consultation	-		
4 th consultation	-		
5 th consultation	-		
PT discussed step goals n/N (%)			
1 st consultation	-		
2 nd consultation	-		
3 rd consultation	-		
4 th consultation	-		
5 th consultation	-		
Self-reported adherence to exercises (EARS) 			
12 weeks	-		
24 weeks	-		
Website access, n/N (%)			
Never		-	
> 1 visit		-	

<sup>1 EARS (Exercise Adherence Rating Scale) range 0-24 with higher scores representing more adherence. SAP version 1.2: Delaware PEAK3/1/24 Page 20 of 38

### 9.4 Efficacy Analyses

The primary and secondary outcomes will be summarized stratified by treatment group at each study timepoint (baseline, 12-week, 24-week). Our primary analysis will use an intention-to-treat (ITT) analysis that includes all participants who wore the monitor for ≥4 days for 10 hours/day at baseline. The statistical model underlying the analysis a mixedeffects model to examine the main and interaction effects of group (Intervention vs. Control) and time (BL, 12-week) on MVPA (minutes/day). The null hypothesis is that there is no difference in change in MVPA in the Intervention group compared to the Control group. The alternative hypothesis is that there is a difference between groups. The nature of the hypothesis is confirmatory as this study has been powered to detect a difference should one exist. The mixed-effect model will be used to calculate the mean and 95% Confidence Interval time in MVPA at each study time point. We will also calculate the difference in means and 95% Confidence Intervals between the Intervention and Control group at each study time point. We will also calculate 2-sided p-values to determine statistical significance of differences between groups by time in MVPA. Data will be summarized by intervention group. Means, Standard Deviations, Minimums and Maximums will be used to summarize continuous variables. Categorical variables will be summarized as frequencies and percentages.

Mixed-effect modeling will be used to estimate MVPA over time. The mixed-effect model using restricted maximum likelihood estimation is a full information approach and leads to unbiased model parameter estimates in the presence of MCAR or MAR missingness. Selection between models with two common covariance structures, Toeplitz and independent errors, will be accomplished using the Akaike Information Criterion (AIC).

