#### Figure 1: Study flow-chart

### 6.2 Inclusion-Exclusion Criteria and General Study Population

(ICH E3;9.3. ICH E9;2.2.1)

In order to be eligible to participate in this study, an individual must meet all of the following criteria:

- 1. Provision of an electronically signed and dated informed consent form
- 2. >45 years of age,
- 3. Resides in the contiguous United States
- 4. Available for the duration of the intervention portion of the study (12 weeks) and willing to wear physical activity monitors
- 5. Looking to move more, i.e., be more active.
- 6. Knee OA diagnosis by the NICE criteria
- 7. Comfortable participating in a program delivered in English
- 8. Is able to safely participate in moderate-intensity exercise as determined by a preexercise screen questionnaire,
- 9. Has either a smartphone or a laptop/desktop computer with an internet connection.
- 10. Has a working email address.

An individual who meets any of the following criteria will be excluded from participation in this study:

- 1. Regularly exercise for more than 60 minutes/week.
- 2. Has a scheduled knee or hip joint replacement
- 3. Has had physical therapy for knee OA in the past 6 months
- 4. Participated in a strength training program for the lower extremities in the past 6 months

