## 8.4 Missing Data

(ICH E3; 9.7.1, 11.4.2.2. ICH E9;5.3. EMA Guideline on Missing Data in Confirmatory Clinical Trials)

Missing data will be given careful attention in the analysis. In this RCT we have two treatment arms and three fixed times for assessment. It is anticipated that drop-outs from the study will be at random because study participants were considered treatment-seeking. However, it is possible that participants may not attend all follow-ups. Drastically fewer participants in the final analysis would affect study sensitivity and excessive missed follow-ups would potentially bias model parameter estimates. Under the assumption of limited data that is missing completely at random (MCAR) or missing at random (MAR), the mixed-effect model using restricted maximum likelihood estimation is a full information approach and leads to unbiased model parameter estimates. Selection between models with two common covariance structures, Toeplitz and independent errors will be accomplished using the Akaike Information Criterion (AIC).

In the event that assumptions are not met regarding missing value frequency, MAR, or MCAR and missing values are occurring with higher frequency or are truly missing not at random (MNAR), the analysis may be biased. To test the missingness assumptions, missing data will first be summarized by group, time, each design cell, and each of the three covariates, age, sex and body mass index in an effort to graphically or tabularly detect patterns in the variation of missingness. More formally, missing/non-missing will be taken as a dichotomous outcome in a logistic regression for continuous covariates and will be compared with between and within factors and sex using chi-square tests. Significant logistic regression coefficients or significant chi-square tests indicate a pattern of missingness variation that will be identified and reported and whose impact on the analysis will be explained if possible. Model residuals will be evaluated for normality using the Shapiro-Wilk test, homogeneity of variance using Levine's test, and transformations, if necessary, will be chosen from among the Box-Cox transformations.

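### No unequal-variance covariance is prespecified for the MVPA model, so the group difference at 12 weeks, and the MAR claim when dropout differs by arm, rest on an unsupported equal-variance assumption

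*SAP*

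**What the plan says.** SAP 9.4 fits a mixed model with group, time and their interaction, for "time (BL, 12-week) on MVPA (minutes/day"). The null hypothesis is "no difference in change in MVPA in the Intervention group compared to the Control group", so the primary contrast is the group-by-time interaction. The same section also asks the model for the "difference in means and 95% Confidence Intervals between the Intervention and Control group at each study time point", and adds: "We will also calculate 2-sided p-values to determine statistical significance of differences between groups by time in MVPA".

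The covariance is chosen as follows: "Selection between models with two common covariance structures, Toeplitz and independent errors, will be accomplished using the Akaike Information Criterion (AIC"). SAP 8.4 repeats this rule, and the same text stands in Protocol 8.4 and 10. No unstructured or heterogeneous form is named, no robust standard error is planned, and the random effects are not stated.

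SAP 8.4 says that REML estimation under MCAR or MAR "leads to unbiased model parameter estimates". It plans a residual check of "homogeneity of variance using Levine's test", followed if needed by a Box-Cox transformation. It does not say whether variances are compared across visits, and it links the check to no change of covariance structure.

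**The concern.** With only these two candidates, AIC cannot detect that the variance changes between visits. Such a change is plausible. Entry excludes people who "Regularly exercise for more than 60 minutes/week", MVPA cannot fall below zero, and one arm is then coached to be more active.

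Two things are at stake. First, intervals at a single visit use a variance pooled over visits, so they are too narrow where the true spread is larger. Second, when follow-up values are missing, the model predicts them from baseline using a slope set by the fitted covariance. If that slope is wrong, MAR alone does not protect the estimate. SAP 9.4 calls the hypothesis confirmatory, so its validity should not depend on an equal-variance assumption that the documents do not support.

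**Working it through.** **Inputs from the documents.** 100 randomized (SAP 7), blocks of 4 (SAP 6.3), and two visits in the primary model (SAP 9.4, 9.5). No SD, correlation, dropout rate or allocation ratio is given, so the plan has no figure to reproduce on this point.

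**Assumptions.** 50 per arm, two-sided 5%, baseline SD s0 = 12 min/day, 12-week SD s1 = 16 or 20 (ratio 1.33 or 1.67), correlation ρ = 0.6, and about 20% missing at week 12 with a log-odds slope of 1 per baseline SD.

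**1. What the equal-variance model fits (two visits, complete data).**
- Variance σ² = (s0² + s1²)/2 = 200 or 272.
- Correlation r = ρ·s0·s1/σ² = 115.2/200 = 0.576, or 144/272 = 0.529.

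**2. Interval for the group difference at 12 weeks.**
- Model SE / true SE = σ/s1 = 14.14/16 = 0.884, or 16.49/20 = 0.825.
- Coverage = 2Φ(1.96 × ratio) − 1 = 91.7% or 89.4%.

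**3. Primary contrast, complete data.**
- True variance of change = s0² + s1² − 2ρ·s0·s1 = 144 + 256 − 230.4 = 169.6, or 144 + 400 − 288 = 256.
- Model value 2σ²(1 − r) = 400 × 0.424 = 169.6, or 544 × 0.4706 = 256.
- The two agree exactly, so the standard error of the difference in change is right.

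**4. Primary contrast, week-12 data missing depending on baseline.** The model estimates each arm's 12-week mean as the completers' mean plus the fitted slope times the gap between the arm's full baseline mean and the completers' baseline mean. The size of an arm's bias is (true slope − fitted slope) × that gap. The true slope is ρ·s1/s0 = 0.8 or 1.0. Under equal variances the fitted slope is the fitted correlation. With 22% missing (logistic intercept −1.5), numerical integration gives a gap of 0.19 SD, or 2.29 min/day.

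| Dropout pattern | Fitted slope | Bias, SD 16 / 20 (min/day) |
|---|---|---|
| Same in both arms | any | 0 / 0 (cancels) |
| Depends on baseline in one arm only | 0.557 / 0.499 | 0.243 × 2.29 = 0.6 / 0.501 × 2.29 = 1.1 |
| Opposite in the two arms | 0.550 / 0.489 | 2 × 0.250 × 2.29 = 1.1 / 2 × 0.511 × 2.29 = 2.3 |

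The bias is negative (effect understated) if the more active intervention participants are the ones lost, and positive if the pattern is reversed. At exactly 20% missing the gap is 2.08 min/day and the biases are 0.5/1.0 and 1.0/2.1. An unstructured matrix recovers the true slope, so the bias is zero in every row.

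**5. Finite-sample check.** REML simulation with 50 per arm, SD ratio 1.5 and correlation 0.6 gave coverage for the difference in change of 92.9% (one arm) and 91.7% (opposite). Unstructured gave 93.7% to 96.3% in every setting tried.

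**6. Spread rising in the intervention arm only.** The true slopes are then 0.8 or 1.0 against 0.6 in controls. With the same dropout in both arms the fitted slope cancels, which leaves −(0.8 − 0.6) × 2.29 = −0.46 or −(1.0 − 0.6) × 2.29 = −0.92 min/day. This is the same under Toeplitz and under a common unstructured matrix. Only an arm-specific covariance removes it.

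**The case against.** The strongest reply is that the primary test is largely untouched. The hypothesis concerns change, step 3 shows its standard error is right with complete data, and the SAP's own Table 3 shell reports between-group change. The visit-specific interval is promised in SAP 9.4 but appears in no SAP table shell. This stands. A reader might infer that the primary 12-week interval is simply wrong, or that the primary contrast is biased whenever data are MAR. The documents support neither reading: bias requires dropout dependence, or variances, that differ by arm.

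Nor do the documents show that follow-up MVPA varies more. The entry criterion concerns regular exercise, not monitor-measured MVPA, and Toeplitz could mean a heterogeneous version. These points stand too, and they make the effect conditional.

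A reader might also infer an inflated type I error in the primary test from a three-visit Toeplitz fit. SAP 9.4 and 9.5 specify two visits for the primary model, and such inflation needs assumed unequal correlations.

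The independent-errors candidate matters little. In simulation AIC chose it in under 1% of trials at a correlation of 0.4 or more. If the unstated random effects include a participant intercept, it would not ignore the correlation at all.

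The Levene and Box-Cox step is only a partial safeguard. Box-Cox needs positive values, while SAP 6.4 allows MVPA of zero, and a transformed analysis leaves the min/day scale of the SAP tables.

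**Conclusion.** The point holds in a limited form. As written, the plan ties every visit to one variance and states unbiasedness under MAR without the condition that the covariance be correctly specified. Under an assumed SD ratio of 1.33 to 1.67, the nominal 95% interval for the group difference at 12 weeks covers about 92% to 89%. The primary difference in change is sound with complete data, and unbiased when variances match across arms and dropout is the same in both. With about 20% missing and baseline-dependent dropout that differs by arm, the bias is about 0.6 to 2.3 min/day, in a direction set by who drops out. Differential dropout is possible because participants are unblinded and only one arm has therapist sessions, but nothing in the documents shows that it will occur. All sizes rest on the assumed SDs, correlation, dropout model and 1:1 allocation. The change is worth making because it is nearly free.

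**What to change.** In SAP 8.4 and 9.4, replace the AIC sentence with a rule along these lines: *an unstructured covariance matrix (3 parameters for two visits, 6 for three) with Kenward-Roger degrees of freedom is used for all outcomes and analysis samples; heterogeneous Toeplitz is used only if the unstructured fit does not converge.*

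- Drop independent errors as a candidate.
- Allow the covariance to differ by arm, at least as a sensitivity analysis, because a common matrix does not remove the bias if spread rises only in the intervention arm (step 6).
- State that the estimates are unbiased under MAR provided the mean and covariance model are correctly specified.

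The cost is a short text change, no new data and a few extra covariance parameters. If the variances are in fact equal, the loss of precision is negligible: the simulated SD of the primary contrast was 2.41 against 2.39 min/day.

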### 9.5 Primary Efficacy Analysis

The primary endpoint of our study is to examine the efficacy of a physical therapist-delivered exercise intervention (Delaware PEAK, referred to as the Intervention) to increase MVPA over 12 weeks compared to a control group receiving web-based resources about knee OA and exercise (referred to as the Control).

The statistical model underlying this analysis is a mixed-effects model to examine the main and interaction effects of *group* (Intervention vs. Control) and *time* (baseline, 12-week) on MVPA (minutes/day).

### 9.6 Secondary Efficacy Analyses

#### 9.6.1 Secondary Analyses of Primary Efficacy Endpoint

The per protocol sample, instead of the ITT sample will be used for the analysis of the primary efficacy endpoint.

#### 9.6.2 Analyses of Secondary Endpoints

The secondary analyses endpoints are to examine the efficacy of a physical therapistdelivered exercise intervention (Delaware PEAK, referred to as the Intervention) to increase treatment beliefs, increase LPA, and increase steps/day over 12 weeks and 24 weeks compared to a control group receiving web-based resources about knee OA and exercise (referred to as the Control). Additionally, we will examine the efficacy of the intervention to increase MVPA over 24 weeks. Both ITT and per protocol samples will be used for separate analyses.

### 9.7 Exploratory Efficacy Analyses

Further, we will explore the efficacy of a physical therapist-delivered exercise intervention (Delaware PEAK, referred to as the Intervention) to decrease VAS pain and increase KOOS subscale scores over 12 weeks and 24 weeks compared to a control group receiving webbased resources about knee OA and exercise (referred to as the Control). Both ITT and per protocol samples will be used for separate analyses. We also will explore the change in exercise adherence from the 12-week to 24-week follow-up timepoints in the Intervention group only. Lastly, we will examine changes in treatment expectations between group from before to after randomization.

# **10 Safety Analyses**

- All-Cause Mortality: A table of all anticipated and unanticipated deaths due to any cause, with frequencies and percentages of such events in each Intervention group will be reported.
- Serious Adverse Events: A table of all anticipated and unanticipated serious adverse events, grouped by organ system, with frequencies and percentages of such events in each Intervention group will be reported.
- Other (Not Including Serious) Adverse Events: A table of anticipated and unanticipated events (not included in the serious adverse event table) that exceed a frequency threshold of 5% within either Intervention group, grouped by organ system, with frequencies and percentages of such events in each Intervention group will be reported.

### 10.1 Adverse Events

We will report on the frequencies and percentages of adverse events that are possibly or definitely related to the study.

# 10.2 Deaths, Serious Adverse Events and other Significant Adverse Events

We will report on the frequencies and percentages of deaths, serious adverse events, and other significant adverse events that are possibly or definitely related to the study.

# **11 Reporting Conventions**

P-values  $\geq 0.01$  will be reported to 3 decimal places; p-values less than 0.001 will be reported as "<0.001". The mean, standard deviation, and any other statistics other than quantiles, will be reported to one decimal place greater than the original data. Quantiles, such as median, or minimum and maximum will be reported to one decimal place.

# 12 Quality Assurance of Statistical Programming (As Applicable)

At the time of this writing, data will be stored on REDCap, a password-protected 2-factor authentication, data management platform hosted by the Center for Human Research Coordination at the University of Delaware.

At the time of this writing, data analysis will be performed using JMP, Version 17.0.0. SAS Institute Inc., Cary, NC, USA.

For quality assurance, all summary score calculations will be performed by REDCap software and checked by a research assistant for accuracy.

# 13 Summary of Changes to the Protocol and/or SAP

Rationale for Adjustments of Statistical Analysis Plan from Protocol (March 12, 2023) The changes from the protocol-specified definitions of aims, outcomes and statistical analytic approaches are outlined below. These changes reflect an error in data collection during the trial. Questionnaires are collected via automated survey in REDCap, and the automated survey did not include the SEE for the 12-week and 24-week follow-up timepoints. Therefore, SEE was only collected at the baseline timepoint and cannot be assessed for change after the intervention.

V0.02 changes: We clarified the definition of adherence to the control and interventions to be included in the per-protocol analysis.

V0.03 changes: We revised section 6.4 to remove a time window for the baseline data collection for the Actigraph since this would not impact follow up time. We removed language around drop outs in section 8.2.1 and 8.2.2 since these subjects would be excluded anyways since they would not have monitor data. Also, we clarified in Table 2 the number of days post-enrollment and post-randomization for follow-up.

V1.0 changes: Revised section 8.2.1 to clarify the ITT sample would include only those with complete baseline monitor data. Added a 24 week follow up to analyses described in sections 10.2.2 and 10.3

V1.1 changes: Revised the study flow diagram. Revised the per protocol sample sets 1 and 2 to a single per protocol sample. Clarified that valid ActiGraph data includes those who wore the monitor for  $\geq$  4 days in section 6.4 instead of in section 8.2. Clarified an index knee for VAS Pain for analysis. Revised secondary data analysis sample (8.2.3) to only include the per protocol analysis and report on outcomes measured with the ActiGraph. Clarified in 8.2.2 that the per protocol sample is a subset of the ITT sample. We clarified in section 5.2 that we are examining health beliefs in physical exercise and physical therapy. We added additional exploratory outcomes. We added exploratory measures from section 5.2 into Table 1 in section 6.4 and removed adverse events as these are listed in section 11.1. We clarified that the EARS will be collected at 12 and 24 weeks in section 6.4. We clarified that both the ITT and per protocol samples will be used for analyses for secondary and exploratory outcomes separately in sections 10.2. and 10.3. Mock tables in section 16 were revised to reflect what is planned for the manuscript.

V1.2 changes: We combined urban area and urban cluster in table 5 since the 2020 Census combined these geographical categories. Replaced supplemental table 4 with tables 4A and 4B, which adds descriptive baseline values (table 4A) in addition to within and between group changes (table 4B). Added a column for non-

randomized to modified supplemental table 5. Added supplemental table 6 to describe sample that had valid MVPA data compared to those who did not have MVPA data. Section 9.3 table 6 modified and added supplemental table 8 to describe treatment fidelity to exercise and education. Renumbered section 9.4 as efficacy analysis and added a calculation of effect sizes for analyses. Added table 4 and supplementary table 9 for effect sizes from the ITT and per protocol analyses, respectively. Added supplementary table 10 for treatment expectations before and after randomization.

